## 9.12 Post-treatment Follow-Up Visits

The post-treatment follow-up period includes the following:

- Survival follow-up: approximately a 2-year period for each patient following the last dose of any study drug.
- During this time, patients will be followed via telephone or other electronic contact at 3-month intervals for follow-up of OS.
- Response status: will be collected every 3 months on all patients who discontinued from study treatment due to reasons other than PD, if they have not initiated any other cancer-directed therapy.

Post-treatment follow-up is performed until the end of study for each patient.

## **10 ASSESSMENT OF PHARMACOKINETICS AND PHARMACODYNAMICS**

### **10.1 Pharmacokinetics Assessments**

Serum concentrations of study drug will be monitored using a quantitative sandwich enzyme-linked immunosorbent assay (ELISA) method in the Sponsor's designated central laboratory. Single and multiple dose PK parameters, maximal concentration ( $C_{max}$ ), time to maximal concentration ( $T_{max}$ ), area under the concentration-time curve from time zero to time T ( $AUC_{(0-T)}$ ), area under the concentration-time curve in a dosing interval ( $AUC_{tau}$ ), area under the concentration-time curve from time zero to infinite time ( $AUC_{(INF)}$ ), trough concentration ( $C_{trough}$ ), clearance (CL), volume of distribution at steady state ( $V_{ss}$ ), and terminal half-life ( $t_{1/2}$ ), will be derived from serum concentration versus time data. Population PK analyses may be conducted using data from this study alone or combined with data from other studies.

Analysis of PK data will be carried out using industry standard software. Population PK modeling may be performed, and an appropriate model and model parameters may be described. Samples will be collected for evaluation of ADA.

### **10.2 Pharmacodynamic/Biomarker Assessments**

#### **10.2.1 Tests Performed for Both Dose Escalation and Cohort Expansion Patients**

Tests to be performed for PD/Biomarker assessments include, but are not limited to, the following:

- Characterization of alterations in serum cytokine levels to include, but not limited to, IFN- $\gamma$ , IL-2, IL-6, IL-10, and TNF- $\alpha$ .
- MGD007 and MGA012 occupancy on PBMCs using multiparameter flow cytometry
- Characterization and comparison of the immune phenotype including PBMCs, B cells, T cells, NK cells, myeloid, and monocytes in peripheral blood and enumeration of T-cell subsets and expression of markers of T-cell activation and/or exhaustion (including, but not limited to, PD-1, CTLA-4, LAG-3, TIM-3, CD25, and markers of cytolytic activity) on PBMCs using multiparameter flow cytometry.
- Determination of immune cell infiltration (including T-cell infiltrate and immunosuppressive myeloid/lymphoid subsets), PD-1, PD-L1, FoxP-3, and gpA-33 and other potential checkpoint/TAMs/regulatory expression levels in archival tumor tissue as it relates to MGD007 and MGA012 antitumor activity will be explored via immunohistochemistry (IHC) staining of archival or contemporaneous tumor biopsy specimens based on specimen availability and applicability.

### **10.2.1.1 Tests Performed for Cohort Expansion Patients Only**

Tests to be performed for PD/Biomarker assessments include, but are not limited to, the following:

- Determination of T-cell infiltration (including but not limited to CD4+ and CD8+ T cells) into the tumor bed of paired pretreatment and on-treatment tumor biopsy specimens. Mandatory pretreatment and on-treatment tumor biopsies will be carried out only during the Cohort Expansion Phase.
- Characterization of T-cell repertoire using T-cell spectratyping on PBMCs and on immune-cellular infiltrate in the tumors done on both pre- and on-treatment tumor biopsy samples depending on tumor response and tissue availability.
- Characterization of transcript profiles in peripheral blood and/or pre- and on-treatment tumor biopsies and archival tumor specimens. Additional genomic profiling approaches and analyses, including, but not limited to, i.e.: NanoString, ctDNA, and mutational load, may be undertaken depending on tumor response and tissue availability.
- Characterization serum biomarkers may be carried out depending on observed antitumor activity.
- To evaluate MGD007 binding to gpA33 and MGA012 binding to PD-1 within tumor tissue from on-treatment biopsy specimens.

## 11 ASSESSMENT OF EFFICACY

### 11.1 Efficacy Assessments

#### 11.1.1 Disease Response Assessments

Tumor assessments will be obtained using CT and/or MRI scans. Target and non-target lesions will be designated at screening and then evaluated at Cycle 1 Day 56 ( $\pm 3$  days), and then every 8 weeks while on study treatment. At each tumor assessment time point, the overall response status will be determined based on assessment of target and non-target lesions as well as appearance of any new lesions. For patients who discontinued from study treatment due to reasons other than documented, confirmed progressive disease, their treating physicians will be contacted every 3 months during post-treatment follow up period about the response status and survival of these patients.

For RECIST v1.1 ([Appendix 5](#)), the overall responses will be categorized as Complete Response (CR), Partial Response (PR), Stable Disease (SD), Progressive Disease (PD), or Not Evaluable (NE). For patients who experience an objective response of CR or PR, responses will be considered unconfirmed until the response has been documented by a subsequent confirmatory scan obtained no less than 4 weeks after the initial scan demonstrating an objective response.

For irRECIST ([Appendix 6](#)), the overall responses will be categorized as immune-related Complete Response (irCR), immune-related Partial Response (irPR), immune-related Stable Disease (irSD), immune-related Progressive Disease (irPD), or immune-related Not Evaluable (irNE). For patients who experience an objective response of irCR or irPR, responses will be considered unconfirmed until the response has been documented by a subsequent confirmatory scan obtained no less than 4 weeks after the initial scan demonstrating an objective response.

For the purpose of patient management, the response determination according to irRECIST will prevail.

For patients who demonstrate acceptable tolerability of treatment with MGD007 and MGA012, and an objective response assessment of irCR, irPR, or irSD, or unconfirmed clinically stable irPD, therapy may be continued.

For patients who are otherwise clinically stable, but have met conventional criteria for PD, therapy may be continued at the discretion of the Investigator pending confirmation of progression at the next scheduled tumor assessment. This approach allows for limited treatment of patients beyond the initial radiographic documentation of disease progression, assuming that patients are tolerating therapy adequately, that patients remain otherwise clinically stable despite this initial radiographic evidence of disease progression and that the Investigator feels the patient may still derive benefit from continuation of therapy. Treatment of patients according to irRECIST principles is supported by well-documented evidence that in some patients treated with T-cell directed, immune-modulatory agents, tumors can evolve

to an objective response after an initial period, characterized by either apparent radiographic growth of target lesions or the development of new target lesions that would otherwise meet the criteria for disease progression using conventional response criteria.

For patients in whom progression is confirmed at the next scheduled tumor assessment, the criteria for irPD will have been met, and treatment with MGD007 and MGA012 should be discontinued. The patient should be removed from study participation after completion of the Post-treatment Follow-up period (see [Section 9.12](#)). However, for individual patients who meet these criteria, but who are otherwise considered to be experiencing clinical benefit in the judgment of the Investigator, consideration may be given to continue treatment with the MGD007 and MGA012 combination, on a case-by-case basis, in consultation with the Sponsor; see [Section 5.4](#).

### **11.1.2 Survival Assessments**

Patients who are discontinued from study treatment will be followed for survival status every 3 months for a 2-year survival follow up period following the final dose of study drug, or until they expire, withdraw consent, or are lost to follow up (see [Section 9.12](#)).

## **11.2 Immunogenicity Assessments**

The generation of ADA directed against MGD007 and MGA012 will be assayed using ELISA method. Blood samples for the immunogenicity assessments will be collected at the time points shown in [Appendix 3](#).

## **12 ADVERSE EVENT REPORTING AND ASSESSMENT OF SAFETY**

The safety assessment will be based on the evaluation of AEs that occur from the time of initiation of administration of study drug through the End of Treatment Visit or 30 days after the last dose of study drug (whichever is later) and will be determined based on signs, symptoms, physical examination findings, and/or laboratory test results from enrolled patients, as appropriate.

Protocol-related AEs and SAEs will be collected from the time the patient has consented to study participation. AEs and SAEs reported between the time the patient signs the informed consent form and the administration of the first dose of study drug will be captured as medical history unless the events are attributed to protocol-specified procedures that are not part of standard of care that occur during this time period, in which case the events will be collected on the SAE Form (as appropriate) and the Adverse Event CRFs.

SAEs considered related to study drug may be reported at any time, even after the patient's final visit.

Progression of the underlying neoplasm resulting in hospitalization or death (e.g., patient hospitalized for or dies from progressive disease [PD] only, without any other SAE) will be documented as an antitumor activity outcome and not as an SAE. If an SAE occurs in a patient and it is unclear whether the event is related to PD, the SAE should be reported.

- A laboratory abnormality should be reported as an AE if it is associated with an intervention. An intervention includes, but is not limited to, discontinuation of treatment, dose reduction/delay, or concomitant therapy. In addition, any medical important laboratory abnormality may be reported as an AE at the discretion of the investigator. This includes laboratory abnormalities for which there are no interventions but the abnormal value(s) suggests a disease or organ toxicity. If clinical sequelae are associated with a laboratory abnormality, the diagnosis or medical condition should be reported (e.g., renal failure, hematuria) not the laboratory abnormality (e.g., elevated creatinine, Urine RBC increased).

### **12.1 Definitions**

#### **12.1.1 Adverse Event**

Adverse event means any untoward medical occurrence in a patient or clinical trial patient associated with the use of a drug in humans, whether or not considered drug related. An adverse event can therefore be any unfavorable and unintended sign (including an abnormal laboratory finding, for example), symptom, or disease temporally associated with the use of a medicinal product, whether or not considered related to the medicinal product.

This includes any occurrence that is new in onset or aggravated in severity or frequency from the baseline condition, or abnormal results of diagnostic procedures, including laboratory test abnormalities.

### 12.1.2 Adverse Drug Reaction

Adverse drug reaction (ADR) is a noxious and unintended response to the medicinal product related to any dose. As used herein, the phrase “response to a medicinal product” means that a causal relationship between a medicinal product and an AE is at least a reasonable possibility.

### 12.1.3 Adverse Event of Special Interest

An adverse event of special interest (AESI) is an event of scientific and medical interest or concern to the Sponsor’s product or program, for which ongoing monitoring and rapid communication to the Sponsor could be appropriate. It may be a serious or non-serious AE, which may require further investigation in order to characterize and understand it.

### 12.1.4 Attribution/Assessment of Causality

Attribution/Assessment of Causality is a determination that describes the relationship or association of the study product with an adverse event.

This assessment of causality or relationship of AEs to the study drug is provided by the investigator and is determined by 1) temporal relationship of the event to the administration of study drug; 2) whether an alternative etiology has been identified, and 3) biological plausibility. Causality must be assessed separately for each study drug.

The causality assessment categories that will be used for this study are described below.

Causality assessments that are considered **not related** to study drug:

*None:* The event is related to an etiology other than the study drug (the alternative etiology should be documented in the patient’s medical record).

*Unlikely:* The event is unlikely to be related to the study drug and likely to be related to factors other than study drug. An alternative explanation is more likely (e.g., concomitant drugs, concomitant disease), or the relationship in time suggests that a causal relationship is unlikely.

If an SAE is considered “unlikely” or “unrelated” to study drug, the Investigator should offer his/her clinical opinion as to what factor(s), agent(s), or process(es) were the likely causative mechanism for the event.

Causality assessments that are considered **related** to study drug:

*Possible:* There is an association between the event and the administration of the study drug and there is a plausible mechanism for the event to be related to study drug; but there may

also be alternative etiology, such as characteristics of the patient's clinical status or underlying disease.

*Probable:* There is an association between the event and the administration of study drug; there is a plausible mechanism for the event to be related to the study drug and the event could not be reasonably explained by known characteristics of the patient's clinical status or an alternative etiology is not apparent.

*Definite:* There is an association between the event and the administration of study drug; there is a plausible mechanism for the event to be related to the study drug, causes other than the study drug is ruled out, and/or the event re-appeared on re-exposure to the study drug.

### **12.1.5 Serious Adverse Event**

A SAE is any adverse event that results in any of the following outcomes:

- Death
- Life-threatening (immediate risk of death)
- Inpatient hospitalization for longer than 24 hours or prolongation of existing hospitalization (even if the event is Grade 1)
- Persistent or significant disability or incapacity
- Congenital anomaly/birth defect
- Important medical events

### **12.1.6 Severity Criteria**

An assessment of severity grade will be made using the National Cancer Institute-Common Terminology Criteria for Adverse Events (NCI-CTCAE) (Version 4.03). The CTCAE are published standardized definitions for AEs to describe the severity of laboratory and organ toxicity for patients receiving cancer therapy. The investigator should use clinical judgment in assessing the severity of events not directly experienced by the patient (e.g. laboratory abnormalities).

For events not contained in CTCAE, the Investigator may assign intensity according to the following generic CTCAE grading scale:

- Grade 1 Mild; asymptomatic or mild symptoms, clinical, or diagnostic observations only; intervention not indicated.
- Grade 2 Moderate; minimal, local, or noninvasive intervention indicated; limiting age-appropriate instrumental activities of daily living (ADL).

- Grade 3 Severe or medically significant but not immediately life-threatening; hospitalization or prolongation of hospitalization indicated; disabling; limiting self-care ADL.
- Grade 4 Life-threatening consequences; urgent intervention indicated.
- Grade 5 Death related to AE.

## **12.2 Adverse Event Collection and Documentation**

### **12.2.1 All Adverse Events**

All patients who receive at least one dose of study drug will be considered evaluable for safety. AEs will be determined based on signs, symptoms, physical examination findings, and/or laboratory test results from enrolled patients as appropriate.

All adverse events whether serious or non-serious, will be reported from the time a signed and dated ICF is obtained until 30 days following the last dose of study drug or until the start of a subsequent systemic anti-cancer therapy, if earlier.

Both protocol-related AEs and SAEs will be collected from the time the patient has consented to study participation. AEs and SAEs reported between the time the patient signs the informed consent form and the administration of the first dose of study drug will be captured as concurrent medical history unless the events are attributed to protocol-specified procedures. Events attributed to protocol-specified procedures will be collected on the Adverse Event eCRFs and Serious Adverse Event form as appropriate.

All adverse events, regardless of seriousness, severity, or presumed relationship to study drug, must be recorded using medical terminology in the source document and the eCRF. All records will need to capture:

- The details of the duration, severity, and seriousness of each adverse event,
- the action taken with respect to the study drug(s),
- the investigator's attribution/causality assessment concerning the relationship of the adverse event to study therapy,
- the outcome of the event.

Whenever possible, diagnoses should be given when signs and symptoms are due to a common etiology (e.g. cough, runny nose, sneezing, sore throat, and head congestion should be reported as "upper respiratory infection"). All treatment measures that are required for adverse event management must be recorded in the source document. The intensity (severity) of adverse events will be assessed using NCI CTCAE (Version 4.03) and serious events will

be determined by the definition provided in [Section 12.1.5](#) above. Generally, all non-serious AEs should be entered into the eCRFs within 5 business days of the sites awareness.

The sponsor assumes responsibility for appropriate reporting of adverse events to the regulatory authorities. The Sponsor will also report to the investigator all suspected unexpected serious adverse reactions. The investigator must report suspected unexpected serious adverse reactions to the appropriate Independent Ethics Committee/Institutional Review Board (IEC/IRB) that approved the protocol, unless otherwise required and documented by the IEC/IRB.

For this study, the patient must be provided with a “wallet (study) card” and instructed to carry this card with them for the duration of the study.

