## 9.11 End of Treatment Visit

A list of evaluations to be performed for the EOTV is provided in [Appendix 1](#); a CT or MRI Scan should be performed during the EOTV, unless a previous scan was performed < 28 days of the EOTV. Criteria for triggering the End of Treatment visit are specified in [Section 5.4](#).

The End of Treatment Visit should be performed after the patient has met off-study criteria. This visit should occur no later than 30 days since the last study dose and before any subsequent anti-cancer treatment. If EOTV < 30 days since the last study dose, the site should contact the patient for safety follow-up no later than 30 days after the last study dose (see [Section 12](#)). It is recognized that certain patients (such as those experiencing progression of disease) may be cared for in facilities other than the participating study site, may proceed to receive other cancer therapy, and/or may elect not to return to the study site. Therefore, this visit is considered optional, but should be carried out whenever possible. All required procedures and tests should be performed if a visit is performed.

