5.2 Safety Endpoints

5.2.1 Adverse Events

Adverse event (AE) means any untoward medical occurrence in a patient or clinical trial patient associated with the use of a drug in humans, whether or not considered drug related. An adverse event can therefore be any unfavorable and unintended sign (including an abnormal laboratory finding, for example), symptom, or disease temporally associated with the use of a medicinal product, whether or not considered related to the medicinal product.

AEs will be captured starting from date of first study drug through end of treatment visit or 30 days following last dose of study drug (whichever is later). Only treatment-related serious AEs will be captured afterwards. These events will be recorded by the Investigators in the eCRFs. Verbatim terms will be coded to lower-level terms using the most recent version of the Medical Dictionary for Regulatory Activities (MedDRA). An assessment of severity grade will be made using National Cancer Institute-Common Terminology Criteria for Adverse Events (NCI-CTCAE) Version 4.03.

AEs reported between the time the patient signs the informed consent form and the administration of the first dose of study drug will be captured as medical history unless the AE is attributable to protocol-specified procedures that are not part of standard of care that occur during this time period, in which case the AE will be collected as AEs on the Adverse Event CRFs. Only treatment emergent adverse events (TEAEs) will be summarized in tables. A TEAE is defined as any event that is newly occurring on or after the administration of

study drug or an event that existed before but increased in severity on or after study drug administration.

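### Protocol 12.2.1 ends AE reporting at new anti-cancer therapy, while Section 12, the Synopsis, Appendix 1 and the SAP do not, so AEs before Day 30 can go uncollected in some patients

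*Protocol*

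**What the plan says.** Protocol 12.2.1 covers serious and non-serious events alike. It starts reporting at signed consent and continues it "until 30 days following the last dose of study drug or until the start of a subsequent systemic anti-cancer therapy, if earlier". This is an earlier-of rule.

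The lead text of Protocol Section 12 bases the safety assessment on events from first dose "through the End of Treatment Visit or 30 days after the last dose of study drug (whichever is later"). The Synopsis and the AE row of Appendix 1 give the same window. SAP 5.2.1 captures AEs "through end of treatment visit or 30 days following last dose of study drug (whichever is later"). This is a later-of rule, and in none of these four places does new therapy end it. The SAP adds: "Only treatment-related serious AEs will be captured afterwards".

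Two neighbouring sections bear on the conflict:

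- **Protocol 12.2.3** narrows SAE reporting to related events only once 30 days have passed since the last dose. It has no cut-off at new therapy.
- **Protocol 9.11** says of the End of Treatment Visit: "This visit should occur no later than 30 days since the last study dose and before any subsequent anti-cancer treatment". If the visit is earlier than Day 30, "the site should contact the patient for safety follow-up no later than 30 days after the last study dose". The section calls the visit optional, because some patients "may proceed to receive other cancer therapy, and/or may elect not to return to the study site".

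On the analysis side, SAP 5.2.1 says "A TEAE is defined as any event that is newly occurring on or after the administration of" study drug, or one already present that then worsens. No end date is given. SAP 6.7.1 tabulates counts and percentages of patients with each event, and SAP 4.1 places every dosed patient in the Safety Population.

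**The concern.** The two rules cannot both be met when new systemic therapy starts before Day 30. A site that follows 12.2.1 may stop recording on the day the new therapy begins. The SAP assumes that collection continued to Day 30 at least.

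The analysis has no means of noticing this. The AE tables are crude proportions with no specified adjustment for time observed, so a patient whose collection stopped early stays fully in the denominator and the uncollected days count as event-free. The open-ended TEAE definition does not impose a common end date on the data either.

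Safety is the primary objective of the escalation phase and a secondary objective of the expansion phase. Protocol 7.5 notes that immune-related events can appear late. The events at risk include non-serious AESIs such as Grade 2 immune-related hepatitis or hypophysitis. Sections 12.2.2 and 12.2.4 require prompt notice of these but set no end of collection of their own.

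**Working it through.** No planned figure depends on this point, so there is none to reproduce. The check compares the rules and then works out when they differ.

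**Notation.** Count days from the last dose of study drug. Let E be the day of the End of Treatment Visit and T the day new systemic anti-cancer therapy starts.

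- End under 12.2.1: min(30, T)
- End under Section 12, Synopsis, Appendix 1 and SAP 5.2.1: max(E, 30)
- Days not covered by 12.2.1: max(E, 30) − min(30, T)

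Since max(E, 30) is at least 30 and min(30, T) is at most 30, the difference is never negative. The 12.2.1 window can be shorter than the SAP window but never longer, so the direction of any bias is fixed.

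| Visit | New therapy | Days not covered |
|---|---|---|
| On time (E ≤ 30) | None before Day 30 | 30 − 30 = 0 |
| On time (E ≤ 30) | Day T < 30 | 30 − T: 16 at T = 14, 9 at T = 21, 2 at T = 28 |
| Late (E > 30, contrary to 9.11) | None before Day 30 | E − 30 |
| Late (E > 30, contrary to 9.11) | Day T < 30 | E − T |

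**Which events fall in the gap.**

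| Event | Position |
|---|---|
| Related SAE | Not lost: reportable without time limit (Protocol 12, 12.2.2, 12.2.3; SAP 5.2.1) |
| Unrelated SAE between T and Day 30 | Outside the window in 12.2.1, reportable under 12.2.3: conflicting rules |
| Non-serious AE, including non-serious AESI, between T and Day 30 | Outside the window in 12.2.1, inside it in the other four places: can go uncollected |
| Event after Day 30, visit on time | Outside both windows (related SAEs apart): unaffected by this conflict |

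**Size.** The documents do not give the share f of patients who start new therapy before Day 30, or when they start. As an illustration only, assume f from 10% to 50%, a common T from 14 to 28, and on-time visits. The share of post-treatment patient-days lost is f × (30 − T)/30:

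- f = 10%, T = 28: 0.10 × 2/30 = 0.7%
- f = 50%, T = 14: 0.50 × 16/30 = 26.7%

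These are shares of days, not of patients with events. The planned tables count patients, so a lost day changes a table only if it holds an event that would have put the patient into a row for the first time. The range therefore does not convert into a change in any reported percentage.

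**The case against.** The best case on the other side has four parts.

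**Safeguards exist.** Section 9.11 places the visit before new therapy and by Day 30, and asks for a safety contact by Day 30 if the visit was earlier, with no exception for patients on new therapy. Related SAEs are never cut off. This stands and narrows the concern considerably. It does not remove it. The visit is optional, and under 12.2.1 a site could make the Day 30 contact and still have no duty to record a non-serious AE that it learned of.

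**The longer rule dominates the text.** It appears in three other parts of the protocol, including the visit schedule, so sites may well follow it. That is possible, but 12.2.1 is the section headed for AE collection, and it is current text. Neither rule can be assumed to prevail at every site.

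**Stopping at new therapy may be deliberate.** Events after a new drug are hard to attribute. That is a fair reason to separate them in the analysis. It does not reconcile the passages, and events never collected cannot be recovered, whereas flagged events can be set aside.

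**The main decisions are little affected.** DLTs run to Cycle 1 Day 42 and are largely on-treatment events, and a single-arm trial has no between-arm bias. This also stands. What remains at stake is the completeness of the descriptive safety tables.

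A reader might also infer a large loss. For example, new therapy on Day 10 costs 20 of 61 + 30 = 91 days, or 22%. The documents do not support this as a trial estimate. Day 10 is an arbitrary choice, and the roughly 61 days comes from the 2.0-month median PFS that Protocol 2.2 quotes for other drugs, not from time on this treatment.

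**Conclusion.** The contradiction is real: when new systemic therapy starts before Day 30, no reading satisfies both rules. Its reach is limited to those patients and to patients whose End of Treatment Visit falls after Day 30 against 9.11. In them, non-serious AEs (including non-serious AESIs) can go uncollected, and unrelated SAEs fall under conflicting instructions. Any bias is towards fewer AEs. Its size cannot be derived, and the 0.7% to 26.7% of post-treatment days rests wholly on assumed shares and timings.

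Three stronger conclusions are tempting and do not follow:

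- **Sites will generally stop early and late toxicity will be under-counted.** With an on-time visit and no new therapy before Day 30, both windows end on the same day, and events after Day 30 are outside both.
- **Most patients move quickly to other therapy.** Section 9.11 says only that certain patients may do so.
- **Residual MGA012 makes the gap serious.** With the mean half-life of 408.9 h in Protocol 2.6.2.1 and simple exponential decay, 2^(−720/408.9) = 0.295, so about 30% remains at Day 30. With an on-time visit both rules have ended by then, so this bears on whether 30 days is long enough, which is a different question.

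**What to change.** - **Protocol 12.2.1:** change only the end-of-collection clause to the rule already in Section 12, the Synopsis, Appendix 1 and the SAP, that is, the later of the End of Treatment Visit and 30 days after the last dose. Keep the start at signed consent. Check the new wording against 12.2.3 so that unrelated SAEs up to Day 30 are under one rule.
- **SAP 5.2.1:** put the same end date in the TEAE definition.
- **SAP 6.7.1 and the AE dataset:** flag, rather than drop, AEs that start after new anti-cancer therapy, and show the tables with and without them.

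The cost is one protocol clause in an amendment, one SAP sentence and one derived flag. The downside is that some AEs caused by the new therapy will be collected. The flag deals with that.
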